resolution(30). There are few studies showing the effectiveness of ketamine administered by intra venous infusion in the treatment of refractory chronic pain medication (29). The recent literature reviews report the results in central neuropathic pain, especially in SCI patients (28,29).

50 to 80 percent of the SCI patients will develop at least an ulcer pressure over a lifetime. These pressure ulcers like all chronic wounds are factors of inflammation. This chronic inflammation in the zone under the injury, often insensitive, is a factor of awareness of the central nervous system. It is common to observe an exacerbation of chronic central neuropathic pain patients during inflammation. On the other hand, the clinical observations report often spectacular efficiency of ketamine on the neuropathic pain in those patients with bedsores.

Is this effect explained by a role on the kynurenine pathway in this population?

Would ketamine be more effective in this population?

Working hypothesis

The hypothesis that we raise, is : ketamine has an anti hyperalgesic action by anti inflammatory effects by interacting with the kynurenine pathway.

We test this hypothesis in a clinical study with ketamine in chronic pain patients with or without associated inflammation. Our choice of population is patients with spinal cord injury with central neuropathic pain. Part of this patient population frequently suffers from pressure sores which leads to chronic inflammation.

Trial purpose and goal:

Our clinical research aims to test the two following hypotheses

(1) The ketamine clinical effects on chronic neuropathic pain are more important when there is an associated inflammation.

(2) Its action is through interaction on the kynurenine pathway.

Methods

Population

The selected population is a population of SCI patients with central neuropathic pain at the level of injury or under injury, chronic (more than three months).

Patients are recruited through specialized consultation pain or bedscares consultation or through consultation and hospitalization in service of physical medicine and rehabilitation in hospital Raymond Poincare in Garches. This hospital is specialised in SCI management. The

Protocol will be proposed in a consultation of usual follow-up or hospitalization. The treatment will be initiated remotely, in a subsequent consultation scheduled apart of their follow-up.

Four groups of patients will be included:

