A temporary stoppage of the study will be considered when new fact (as defined above) in order to give himself time to reassess the balance of benefits and risks of research jointly with ANSM .

Ratings criteria

Main evaluation criterion

Decrease (more than 30%) the intensity of neuropathic pain evaluated at the moment on a numeric scale of 10 points between H0 and H4.

Secondary evaluation criteria

Score of NPSI on H0, J1, J4, J7 Under the NPSI score; H0, J1, J4, J7 Score of depression HADS or Hamilton J0, J7 Pain timeline between J0 and J7. Painful surface evaluated on mapping H0, J1, J4, J7 Decrease in scores between baseline and H4. Side effects of the drugs evaluated H0 and H4 of the end of the infusion then in J1. Auto assessment of relief of pain and mood improvement at 7 days after infusion. Blood assays pre administration of Ketamine then H4 after end of Directors of: serotonin (5-HT), kynurenine (KYN), indoleamine 2, 3-dioxygenase 1 (IDO1) activity (ratio KYN/TRP), kynurenic acid (KA) and quinolinic acid (QA), as well as 3 proinflammatoires cytokines it- 1β , IL-6, and TNF - α

Patient selection, exclusion and data collected.

The criteria for inclusion:

- SCI with central neuropathic pain with or without bed sores.
- Adults speaking and understanding the French
- With chronic neuropathic pain, according to the IASP definition
- Painful intensity > or = 6 / 10 during the week prior to the inclusion
- Spinal cord injury a few either the origin (traumatic, degenerative, tumor, post operative), responsible for paraplegia in a chronic state.
- Able to give their informed consent after a clear, fair and appropriate information
- Having given their agreement by a written consent signature.

No inclusion criteria:

- Patients with a hypersensitivity to ketamine or one of its excipients.
- Another Interventional trial participation, or participation in another trial interrupted for less than 3 months.

- Patient unable to give their consent
- Pregnancy or lactation underway
- Refusal of consent signature
- Cardiovascular diseases particularly associated with rhythm disorders and severe heart failure, coronary, discovered by examination, ECG or biological assessment or known.
- HTA unstabilized > 180/100 mmHg
- Severe hepato cellular and / or renal failure.
- For the group without sores, lack of ongoing inflammatory pathology noted by the interrogation (fever, sepsis, urinary tract infection)

Exclusion criteria:

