In the follow-up phone calls and self-report at home will be considered follow-up. Missing data management has already been clarified above.

Assessment of treatment effectiveness

The effectiveness of the treatment will be judged on a reduction of more than 30% of the intensity of neuropathic pain evaluated at the moment on a numeric scale of 10 points between H0 (before infusion) and H4 (after the end of the infusion). This criterion will be assessed by one of the investigators of the study.

Assessment of the safety of the treatment

Infusion being made in recovery room, the usual follow-up of a patient in recovery room will be arranged: decision-making of the constants every 15 minutes including the oxygen saturation, blood pressure, heart rate, awareness of Glasgow score, the respiratory rate. Supervision of one hour after the end of the infusion will be implemented.

The release of recovery room will be one hour after the end of the infusion and with the usual criteria of output with Aldrete score.

Any adverse event during infusion will be reported to a doctor Anaesthesiologist resuscitator and will be declared.

If an adverse event occurs a period of hospitalization is equal to 5 times the half-life (3 hours about ketamine), more than 15 hours will be organized until total elimination of the product.

Sample size and statistical analysis

After data from a study underway by our team (study LIKE), the standard deviation of instant pain score is of 1.4 on the same model. We considered that an improvement of 30% in the score of the intensity is relief significant clinic. Based on these figures and assuming a risk $\alpha = 0.05$ and a risk $\beta = 0.90$, and using a one-sided Student's T test for a comparison of the 2 to 2 groups the minimum calculated sample size is 12 patients analyzed per group (for a total of 48 patients).

After checking the normality of distributions, comparison of continuous variables (Score, NPSI, pain, depression and biology Score) between the two groups will be analyzed with the Student's T test, variables with a no normal distribution will be analyzed with the non-parametric Mann-Whitney U test. p < 0.05 was considered statistically significant p-values. R and SPSS software will be used for the production of statistics.

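### An unspecified normality check picks the t test or Mann-Whitney after the data are seen, so the effect measure is not fixed and may differ between the bedsore strata

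*Combined protocol and SAP*

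**What the plan says.** The section on sample size and statistical analysis of the combined protocol and SAP gives one rule for all continuous outcomes. It begins "After checking the normality of distributions, comparison of continuous variables (Score, NPSI, pain, depression and biology Score) between the two groups" by Student's t test, and adds that "variables with a no normal distribution will be analyzed with the non-parametric Mann-Whitney U test". It does not say which normality test is used, at what level, or on what unit. The same section plans an interim analysis by the end of April 2018 on the same criteria as the final one.

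The trial has four groups of 12: ketamine or placebo, with or without bedsore. The sample size was found "using a one-sided Student's T test for a comparison of the 2 to 2 groups". The first hypothesis under the trial purpose and goal is: "The ketamine clinical effects on chronic neuropathic pain are more important when there is an associated inflammation". No analysis that contrasts the two bedsore strata is described.

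**The concern.** A t test compares means and Mann-Whitney compares ranks. If the data decide between them, the quantity being estimated is unknown until the data are in. The first hypothesis needs the ketamine effect in each stratum on one scale. A mean difference in one stratum and a rank result in the other cannot be contrasted.

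The check is also poorly suited to these data. Pain on a 10-point scale with an SD of 1.4 takes few distinct values, so a formal test can reject because of ties even where the t test is sound. For skewed concentrations, 12 patients are too few to detect the skew reliably, so the raw-scale t test may be run on data better analysed on logs.

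**Working it through.** **1. The plan's sample size.** The SD input is "the standard deviation of instant pain score is of 1.4 on the same model". The target effect is a 30% reduction in pain, which the plan takes as clinically meaningful relief, and the test is one-sided. The section writes "assuming a risk $\alpha = 0.05$ and a risk $\beta = 0.90", while the study summary gives 1 − β = 0.90, so power 0.90 is used. No baseline mean is given. Assumption: 6, the entry floor ("Painful intensity > or = 6 / 10 during the week prior to the inclusion"), so δ = 0.30 × 6 = 1.8.

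- Normal approximation: n = 2 × 1.4² × (1.645 + 1.282)² / 1.8² = 10.4, rounded up to 11.
- Exact noncentral t: n = 12 per group, with power 0.920 at 12.

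The plan's 12 per group is reproduced.

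**2. How often the check rejects.** This was simulated with 8,000 strata per scenario: normal scores, rounded to whole numbers (an assumption) and kept within 0 to 10, 12 per arm, each check at 5%. At SD 1.4, Shapiro-Wilk rejects in 21% to 22% of single arms, against 4.8% for continuous normal scores. The excess comes from rounding. If either arm failing sends the stratum to Mann-Whitney, q = 1 − (1 − 0.215)² = 0.38, which matches the simulated 38% to 39%.

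**3. How often the strata get different tests.** With a separate choice per stratum, P(different) = 2q(1 − q). At q = 0.39 this is 2 × 0.39 × 0.61 = 0.48. For a common q the ceiling is 50%, reached at q = 0.5.

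| Reading | P(different tests) |
|---|---|
| Whole numbers, SD 1.4, each arm, Shapiro-Wilk | 47–48% |
| Same, Lilliefors | 49% |
| SD 1.4, the 24 pooled, Shapiro-Wilk | 33–49% |
| SD 1.4, the 24 pooled, Lilliefors | 44–50% |
| SD 1.4, residuals, Shapiro-Wilk | 29–30% |
| SD 1.4, residuals, Lilliefors | 47% |
| SD 2.0, each arm, Shapiro-Wilk | 32–35% |
| SD 2.5, each arm, Shapiro-Wilk | 26–34% |
| SD 2.0 to 2.5, residuals, Shapiro-Wilk | 12–18% |
| Continuous normal scores | 7–19% |
| One choice per variable for the whole trial | 0% |

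**4. Error rates for pain** (6,000 strata, whole-number scores, SD 1.4; two-stage choice by the check).

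| | Always t | Always Mann-Whitney | Two-stage |
|---|---|---|---|
| Type I error, one-sided 5% | 5.2% | 5.1% | 5.4% |
| Power, δ = 1.8, one-sided | 0.909 | 0.895 | 0.907 |
| Power, δ = 1.8, two-sided | 0.835 | 0.810 | 0.827 |

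The two-sided row is shown because the analysis rule does not state sidedness. One-sided power is below 0.920 because rounding adds variance: 1.96 + 1/12 = 2.04, an SD of 1.43. One-sided, the two tests reach different verdicts in 1.6% of strata under no effect and 2.7% under δ = 1.8. Two-sided, the figures are 1.8% and 4.4%.

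**5. Markers.** Assumptions: lognormal values, a two-fold difference, 12 per group.

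| Log-SD | Two-stage power | t on logs | Loss |
|---|---|---|---|
| 0.5 | 0.891 | 0.903 | 1.2 points |
| 0.7 | 0.611 | 0.643 | 3.2 points |
| 1.0 | 0.346 | 0.375 | 2.9 points |

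At log-SD 0.7, Shapiro-Wilk misses the skew in 51% to 52% of groups. Repeat runs at that value gave losses of 2 to 3 points.

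**The case against.** The rule speaks of variables, and the literal reading is one choice per outcome for the whole trial. The strata then never get different tests. Whole-number scoring is not stated either.

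The simulated quantity is the H4 score, whereas the main criterion is a decrease between H0 and H4. Simulated change scores gave 17% to 47% and percent change 31% to 45% (4,000 sets, Shapiro-Wilk on arms or residuals, assumed baseline mean 6.5 and H0–H4 correlation 0 or 0.5). If the more-than-30% decrease is a yes/no responder outcome, neither test applies to the primary endpoint.

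The rule was written in advance and the statistician is blind to group, which limits choosing a test to favour ketamine. Error rates barely change. And because no between-stratum contrast is planned, matching tests would not by themselves answer objective 1.

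All of this stands as a limit on the size of the problem. None of it supplies the missing test, level or unit. The pairwise framing of the sample size makes a separate choice per stratum a natural reading too, and the text does not exclude it. Blinding reduces the scope for bias but does not fix the effect measure.

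**Conclusion.** The rule leaves the effect measure unfixed until the data are seen, and it may leave it different in the two strata. The figure of about 48% holds only with whole-number scores at SD 1.4, Shapiro-Wilk at 5% on each arm, either failure sending the stratum to Mann-Whitney, and a separate choice per stratum. The range across readings is 0% to about 50%.

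A reader might infer three stronger conclusions that the documents do not support:

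- **An even chance of mismatched tests as a property of the plan.** The plan never says the choice is made per stratum.
- **A distorted type I error or materially weaker pain analysis.** The two-stage rule stays near 5%, and power falls by 0.2 points one-sided and 0.8 two-sided.
- **Different tests as what blocks objective 1.** Two within-stratum p-values do not test a difference in effects even when both come from the same test. That needs a treatment-by-bedsore term.

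The harm is an effect measure left to an undefined check, which may not support the contrast objective 1 needs. There is also a small power loss on skewed markers, which rests on assumed log-SDs and an assumed two-fold difference. It should be corrected, but it does not invalidate the trial.

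**What to change.** Delete the normality check and fix the analyses in advance, for the April interim as well as the final analysis:

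- **Pain, NPSI and HADS:** one linear model across all four groups with treatment, bedsore stratum, their interaction and the baseline score. Report the ketamine effect in each stratum and the interaction with confidence intervals. Use a rank or permutation analysis as sensitivity only.
- **Markers and KYN/TRP:** the same approach on the log scale, reported as ratios of geometric means.
- **Primary endpoint:** state whether it is a mean score or a more-than-30% responder outcome, since the linear model does not serve a yes/no endpoint.

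This changes wording only, with no extra patients or assays. Marker results will be read as fold-changes, and values below the assay limit need a fixed substitution rule.

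Naming the interaction does not make it precise. Before baseline adjustment its standard error is 1.4 × √(4/12) = 0.81, against 1.4 × √(2/12) = 0.57 for the ketamine effect within one stratum. The plan should say so.

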For hospitalized patients, their usual follow-up will be resumed after the release of recovery. Inclusion in the study lasts 7 days in total, with a follow-up by phone and by a tracking notebook, the last phone call held at 7 days of infusion.

Description of study stop, rules or criteria of exclusion for subjects.

All serious adverse events, defined by: ketamine or its excipients, shock, pushed hypersensitivity reaction hypertensive greater than 180/110 defined as hypertensive emergency according to the HAS, a depression respiratory causing a desaturation < 92% in air, a marked psychodysleptique reaction causing a major stir, that can be linked to the administration of the product will immediately stop the infusion, supported by a doctor specializing in Anaesthesia-resuscitation and the statement from pharmacovigilance and the ANSM.

Each observation will include a reporting of serious adverse events card.

The patient will be analysed in the study for intention to treat analysis, the last pain expressed will be chosen as main analysis on which the study will be judged.

Per-protocol analysis will also take place, excluding patients who have not benefited from the full dose of ketamine.

Any withdrawal of consent before the infusion will result in the exclusion of the subject of the study.

Withdrawal of consent after the end of the infusion, will lead to the choice of the subject, an analysis by intention to treat if the patient accepts the conservation of already saved data or also if it wishes the ouster of the subject of the study so that the deletion of all the data related to the patient, in agreement with the notion of free consent informed, revocable at any time.

The study will end permanently after the 48th patient tracking.

Is 7 days after the inclusion and treatment of the 48th patient (see calculation of the number of subjects needed here below)

Safety assessment and management of serious events

The investigator has the responsibility to report every adverse events.

Definitions

Adverse event : any harmful event occurring in a person who lends itself to biomedical research, that this event is related to research or the product on which this research is defined as adverse event

Side effect: all adverse event due to research.

We class them in subclasses:

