As part of a master of Pharmacology 2 to be made for may 2018, an interim analysis will be carried out by end April 2018, that this will have the same criteria as the final analysis. A security assessment will be also carried out at this time and an assessment of the derivatives to the Protocol.

Both analyses above cited will be intention to treat, all randomized subjects will be included. Management of the lost will be extrapolating value worst case being investigated for missing data. Patients withdrawing consent during the study without desiring the removal of their data will be analyzed. If an application for withdrawal with withdrawal of the data then patients won't be analyzed.

Access to the sources and documents related to the research.

Protection of research participants will be an anonymisation of the data recording in secure files. A declaration to the CNIL has been registered for this search No. 2122369 v 0 as of November 21, 2017.

Access to the source file, anonymised data collection will be left in an audit requested on the study.

Quality control and Assurance

For our study insurance civil liability promoter of Interventional research under article L 1121-1 of the Code of public health is subscribed to hospital society of mutual assurances with the number of contract No. 124.626.

To ensure quality control satisfactory we will put in place standardized operating procedures (POS) with standardized patients support instructions given to investigators of the study. Each patient will have a specification of anonymized observation which will include all identified information, the collection different scores used in the study as well as a record of serious adverse event reporting. These notebooks of observation will be kept throughout the study and one year after the end (last patient included either 7 days after the end of the 48th patient inclusion).

Direct benefit:

Patients will be able to benefit from treatment with ketamine and the support and follow-up pain specialist for their refractory neuropathic pain.

If patients included in this study have a real clinical benefit, this treatment may be proposed outside the clinical trial. Then, they will be given priority in the queue.

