For society this study will allow progress in the potential effectiveness of ketamine on chronic pain, hypothesis put forward in cancer pain and other chronic pain but for which we still lack of data sufficient to prove its benefit. It will also standardize administration protocols and avoid prolonged high doses of ketamine over several weeks that is responsible of serious adverse (36).

In addition it will better understand the mechanism of action of the product on this type of pain.

Risks incurred and constraints:

Ketamine at a dose of 1 mg / kg is well tolerated in the clinic and in the various studies around ketamine.

The contraindications of ketamine are allergy, severe hypertension, severe heart failure: patients excluded from our study.

In the conditions of the study, dosage and duration of infusion, the risk of adverse effect is minimal.

The constraints for our patients will include:

Learn about 48 h of infusion a diet serotonin (avoid the bananas in particular) and tryptophan (chocolate to be avoided).

Come to the appointment for the administration of infusion.

Inform the doctor of the research of the use of any medication, as well as of any event occurring during the search.

An accompanying person for the return home for patients on an outpatient basis. Do not take part in another Interventional trial for the duration of the study. Being affiliated to a social security scheme or equivalent.

Agenda forecast

- May June 2017: finalization writing project, application to tender
- September 2017-December 2017: registration of the candidate in MASTER
 2, and theoretical courses in parallel, finalisation of the project and administrative procedures (Committee of protection of individuals, filing ANSM, CNIL)
- January 2018 may 2018: Inclusion of patients and first report on the effectiveness on the first patients included with interim analysis end of April / beginning of may 2018.
- End of year 2018: writing article and dissemination of results at the Congress of pain, anesthesia
- Early 2019: Finalization of article and submission to a journal international

Expected end-of-project results:

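### The April 2018 effectiveness analysis is not declared non-confirmatory, and nothing keeps its between-arm results from investigators who still enrol and assess patients

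*Combined protocol and SAP*

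**What the plan says.** **Interim.** Under Sample size and statistical analysis, the plan says that for a Master 2 due in May 2018 "an interim analysis will be carried out by end April 2018, that this will have the same criteria as the final analysis". A safety review and a review of protocol deviations are listed as additional items. The next paragraph adds that "Both analyses above cited will be intention to treat, all randomized subjects will be included". Agenda forecast puts inclusion in January to May 2018 and describes the output as a "first report on the effectiveness on the first patients included with interim analysis end of April / beginning of may 2018".

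**Threshold and test.** The analysis text gives one threshold: "p < 0.05 was considered statistically significant p-values". It does not say whether tests are one-sided or two-sided. One-sided testing appears only in the sample-size calculation: "using a one-sided Student's T test for a comparison of the 2 to 2 groups".

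**End of study.** The section on stopping rules says: "The study will end permanently after the 48th patient tracking". No rule ends the trial early for efficacy.

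**Blinding and assessment.** Design of the study keeps the patient, the evaluating clinician and the statistician blind to group, and keeps the blind for the whole study. Only the nurse who prepares the syringe knows the envelope's contents. Of the primary pain criterion, Assessment of treatment effectiveness says: "This criterion will be assessed by one of the investigators of the study". No oversight committee is planned.

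**The concern.** Two things are left open.

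The first is the status of an April p-value. The word criteria may mean only endpoints, since the Ratings criteria section uses it that way ("Main evaluation criterion"). On either reading, the same effectiveness question is put to the data twice, 0.05 is the only level available, and no text ranks the two analyses. A significant ketamine-placebo difference in the May thesis could then stand as an efficacy finding that the full trial does not bear out.

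The second is who sees the comparison. Blinding of allocation does not stop a group A versus group B difference, or one with the arms named, from being computed and circulated. Investigators who know that a difference has emerged may hold different expectations while they enrol later patients and collect a self-rated pain score. This is a risk of bias, not a demonstrated effect.

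**Working it through.** **1. The plan's own figure.** Inputs: SD 1.4, 30% improvement, one-sided alpha 0.05, power 0.90 (given as power in the study summary; the analysis section labels 0.90 as beta). The absolute difference is not stated. Assuming a baseline at the entry threshold of 6/10, it is 0.30 × 6 = 1.8 points.

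- Normal approximation: n = 2 × (1.645 + 1.282)² × 1.4² / 1.8² = 10.4, so 11 per group.
- Exact t calculation: 12 per group, with power 92.0% at n = 12.

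The stated 12 per group (48 in total) is reproduced with a one-sided test at 0.05, so that is the main case below.

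**2. Information at the April look.** The number of patients is not given. The primary endpoint is read at H4, so follow-up adds almost no lag. Assuming even accrual from January:

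- Six months of inclusion (study summary): f = 4/6 = 0.67, with 48 × (1 − 0.67) = 16 patients still to come.
- January to May (Agenda forecast): f = 4/5 = 0.80, with 48 × 0.20 = 9.6, about 10, still to come.

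**3. The final test alone.** With no efficacy stop, all 48 patients are analysed whatever April shows. The final test's error is 5%. In simulated t tests with 12 per group it was 5.0% to 5.1%.

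**4. If a significant April result is also reported as efficacy.** Under the null, the interim and final statistics are approximately bivariate normal with correlation √f. For one ketamine-placebo comparison:

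Error = 1 − P(Z₁ < 1.645 and Z₂ < 1.645)

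| | f = 0.67 | f = 0.80 |
|---|---|---|
| Correlation √f | 0.816 | 0.894 |
| P(neither significant), one-sided 0.05 | 0.9258 | 0.9314 |
| Error at either look, one-sided | 7.4% | 6.9% |
| April significant, final not | 7.42 − 5 = 2.42% | 6.86 − 5 = 1.86% |
| Share of false-positive April results not confirmed | 2.42/5 = 48% | 1.86/5 = 37% |
| Error at either look, two-sided 0.05 | 7.7% | 7.1% |
| Part of it favouring ketamine (half) | about 3.85% | about 3.5% |

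Simulated t tests agree with the one-sided figures: 7.6% with 8 of 12 per group at the interim, and 6.8% with 10 of 12.

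**5. Access.** Set side by side, the blinding text says who may know a patient's allocation, and the interim text says an effectiveness analysis will be done for a thesis. Neither says who receives group-level results, coded or named.

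**The case against.** The strongest reply is that no error-control failure exists. The trial runs to the 48th patient, the final test keeps its level, and the 7.4% needs a rule that the plan never states, namely that significance at either look counts. That is right. A reader might infer that the plan itself inflates the trial's type I error to 7.4%, but the documents do not support this.

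The plan also implies a ranking. It distinguishes interim from final, schedules article writing for the end of 2018, and calls the whole study preliminary. This weakens the concern, but the agenda still promises an effectiveness report in the spring and no sentence limits what that report may claim.

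If testing is two-sided, the chance of a false claim for ketamine over both looks is about 3.85% or 3.5%, below the one-sided 5% used for planning. This stands, since sidedness is stated only for the sample size.

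A reader might take a higher error, about 8.3%, by treating January to October 2018 as the inclusion period (f = 0.40). The summary gives those dates as the start and end of the study, not as inclusion.

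On access, a reader might infer that the April look breaks the blind, or that the thesis author scores the patients. Neither is stated. The statistician working during the study is blind to group, so releasing named-arm results would itself conflict with the written blind. One listed principal investigator is in a pharmacology Master 2, but that this person writes the thesis and also enrols or scores patients is an inference. What remains is narrower: release of aggregate results, above all coded ones, is not governed.

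**Conclusion.** The point holds as a gap in reporting status and in access to results. It is not a flaw in the final test. The plan sets up an effectiveness comparison during inclusion, with 0.05 as the only threshold, and does not subordinate it to the 48-patient analysis or keep its between-arm results from enrolling and assessing investigators.

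The size is conditional. The 7.4% and 6.9% apply only if a significant April result is also reported as efficacy. They cover a single ketamine-placebo comparison and rest on even accrual and one-sided testing at 0.05 at both looks. On the same one-sided terms, between about a third and a half of false-positive April results would not survive to the final analysis. The possible effect of early knowledge on later pain scores cannot be quantified from the documents. The change is worth making before the April look. Confidence is medium, because the interim size, the sidedness of the tests and the roles of the people involved are not stated.

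**What to change.** In Sample size and statistical analysis, replace the clause giving the interim the final analysis's criteria, and align Agenda forecast with it. The new text should say:

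- The analysis of all 48 patients is the only confirmatory analysis.
- Any between-arm result from April 2018 is descriptive and carries no significance claim. Without an early stop, no interim significance level is needed.
- Between-arm results, coded or named, are withheld from anyone who enrols or assesses patients until the 48th patient completes J7. A thesis that contains them is withheld from those people for the same period.
- Otherwise the April report covers recruitment, protocol deviations, safety and data pooled over all groups.

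The cost is that the May 2018 thesis carries no confirmatory efficacy claim and, if its author enrols or assesses patients, reports pooled data only. If a between-arm look is kept, someone outside enrolment and assessment must run it and hold the results. Sample size and final test are unchanged.
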